Day Relative to Randomization	Can be done any time prior to complete screening	-49 to -1	
Tolerance Interval for Visit (Days)	Can be done at any time	≤49 before V2	
Screening PET Scans and MRI			
Florbetapir F18 PET scan		X	The participant should meet all other non-imaging eligibility criteria before the screening florbetapir F18 PET scan. Previous florbetapir F18 PET scans within 3 months of randomization may be acceptable. The acceptance of a historical scan is at the discretion of the sponsor.
MRI		X	The participant should meet all other non-imaging eligibility criteria before the screening MRI.

Abbreviations: ApoE = apolipoprotein E; CDR = Clinical Dementia Rating; C-SSRS = Columbia-Suicide Severity Rating Scale; ECG = electrocardiogram; IWRS = interactive web response system; MMSE = Mini-Mental State Exam; MRI = magnetic resonance imaging; PET = positron emission tomography; V = visit.

Visits 2 through 11

	Open-Label Study Period										Comments
Visit Number	2	3	4	5	6	7	8	9	10	11	
Weeks relative to first infusion	0	4	8	12	16	20	24	28	32	36	
Visit interval tolerance (days)		-7 to +10	±7	±7	±7	±7	±7	±7	±7	±7	
Entry and Administrative											
Inclusion and exclusion criteria, review and confirm	X										Inclusion and exclusion criteria should be confirmed at V2, prior to randomization and administration of the first dose of study intervention.
Randomization	X										
Brief Physical/Neurological Exam	X			X			X			X	As described in the Manual of Operations. Any clinically significant changes from baseline on brief physical/neurological examinations should be noted on the AE CRF.
Concomitant medications	X	X	X	X	X	X	X	X	X	X	
AEs	X	X	X	X	X	X	X	X	X	X	Any events that occur after signing the informed consent are considered AEs as defined in Section 10.3.
C-SSRS screening/baseline	X										
C-SSRS since last assessment			X		X		X		X		
Administer study intervention	X	X	X	X	X	X	X	X	X	X	See Section 6.1. Administration of study intervention (and treatment-related activities conducted in person) outside of the visit window is not a protocol deviation, unless 2 doses are administered within <21 days of each other. The participant should be observed for a minimum of 30 minutes following the end of each infusion.

	Open-Label Study Period										Comments
Visit Number	2	3	4	5	6	7	8	9	10	11	
Weeks relative to first infusion	0	4	8	12	16	20	24	28	32	36	
Visit interval tolerance (days)		-7 to +10	±7	±7	±7	±7	±7	±7	±7	±7	

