PK sample							X				Collect prior to infusion. Predose collections may be collected from the IV site prior to the infusion.
Immunogenicity (ADA) samples	X						X				Collect prior to infusion.
Stored Samples											
Genetics sample	X										Collect prior to infusion.
Exploratory biomarker samples	X						X				Collect prior to infusion.

Abbreviations: ADA = anti-drug antibody; AEs = adverse events; CRF = case reporting form; C-SSRS = Columbia-Suicide Severity Rating Scale; MRI = magnetic resonance imaging; PET = positron emission tomography; PK = pharmacokinetic; V = visit.

Visits 12 through 21 and Follow-Up

	Open-Label Treatment											Short-term Follow-up	Comments
Visit Number	12	13	14	15	16	17	18	19	20	21	ET	801-804^	^Visit 801 to 804 may be used for return to baseline ADA monitoring and other safety assessments at discretion of the sponsor and may be requested within the time period listed.
Weeks relative to first infusion	40	44	48	52	56	60	64	68	72	76	-	84-120	
Visit interval tolerance (days)	±7	±7	±7	±7	±7	±7	±7	±7	±7	±7	-	±14	
Entry and Administrative													
Brief Physical/Neurological Exam				X			X			X	X	X	As described in the Manual of Operations. Any clinically significant changes from baseline on brief physical/neurological examinations should be noted on the AE CRF.
Concomitant medications	X	X	X	X	X	X	X	X	X	X	X	X	
AEs	X	X	X	X	X	X	X	X	X	X	X	X	Any events that occur after signing the informed consent are considered AEs as defined in Section 10.3.
C-SSRS since last assessment	X		X		X		X		X		X	X	

	Open-Label Treatment											Short-term Follow-up	Comments
Visit Number	12	13	14	15	16	17	18	19	20	21	ET	801-804^	^Visit 801 to 804 may be used for return to baseline ADA monitoring and other safety assessments at discretion of the sponsor and may be requested within the time period listed.
Weeks relative to first infusion	40	44	48	52	56	60	64	68	72	76	-	84-120	
Visit interval tolerance (days)	±7	±7	±7	±7	±7	±7	±7	±7	±7	±7	-	±14	
Administer study intervention	X	X	X	X	X	X	X	X	X	X			See Section 6.1. Administration of study intervention (and treatment-related activities conducted in person) outside of the visit window is not a protocol deviation, unless 2 doses are administered within <21 days of each other. The participant should be observed for a minimum of 30 minutes following the end of each infusion.

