4.1. Overall Design

Study AACN is a multicenter, randomized, open-label, head-to-head, Phase 3 study of donanemab compared to aducanumab in participants with early symptomatic AD.

Participants who meet entry criteria will be randomized in a 1:1 ratio to 1 of the following treatment groups:

- donanemab: 700 mg IV Q4W for first 3 doses and then 1400 mg IV Q4W
- aducanumab: refer to PI/routine clinical practice

The maximum total duration of study participation for each participant, including screening and the post-treatment follow-up periods, is up to 127 weeks:

- Lead-In: any time prior to complete screening
- Complete Screening: up to 7 weeks
- Open-label study period: 76 weeks
- Follow-Up: up to 44 weeks

The maximum duration of treatment is 72 weeks.

Scheduled Reduction of Donanemab

Participants randomized to donanemab whose amyloid plaque reduction as measured by florbetapir F18 PET scans at Visit 8 (Week 24) or Visit 15 (Week 52) meets criteria will stop donanemab infusions but continue all other assessments for the remaining duration of the open-label period and short-term follow-up period. These dose reduction rules are defined by the sponsor.

Participants randomized to aducanumab will continue monthly infusions throughout the open-label period, regardless of amyloid plaque reduction on florbetapir F18 PET scans.

Change in amyloid burden (as assessed with florbetapir F18 PET by personnel blinded to treatment allocation) will be compared in donanemab and aducanumab-treated participants.

Participant randomization will be stratified by amyloid burden and ApoE ϵ 4 status (noncarrier/heterozygous/homozygous).

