8.2.4. Suicidal Ideation and Behavior Risk Monitoring

Participants being treated with study intervention should be monitored appropriately and observed closely for SIB or any other unusual changes in behavior, especially at the beginning and end of the course of intervention, or at the time of dose changes, either increases or decreases. Participants who experience signs of SIB should undergo a risk assessment. All factors contributing to SIB should be evaluated and consideration should be given to discontinuation of the study intervention.

Baseline assessment of SIB and intervention-emergent SIB will be monitored during Study AACN using the C-SSRS.

C-SSRS

C-SSRS is a scale that captures the occurrence, severity, and frequency of SIB during the assessment period via a questionnaire. The scale was developed by the NIMH trial group for the purpose of being counterpart to the C-CASA categorization of suicidal events.

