8.3.1. Timing and Mechanism for Collecting Events

This table describes the timing, deadlines, and mechanism for collecting events.

Event	Collection Start	Collection Stop	Timing for Reporting to Sponsor or Designee	Mechanism for Reporting	Back-Up Method of Reporting
Adverse Event					
AE	Signing of the ICF	Participation in study has ended	As soon as possible upon site awareness	AE CRF	N/A
Serious Adverse Event					
SAE and SAE updates – prior to start of study intervention and deemed reasonably possibly related with study procedures or occurring after receiving PET tracer	Signing of the ICF	Start of intervention	Within 24 hours of awareness	SAE CRF	SAE paper form
SAE and SAE updates – after start of study intervention	Start of intervention	Participation in study has ended	Within 24 hours of awareness	SAE CRF	SAE paper form

Event	Collection Start	Collection Stop	Timing for Reporting to Sponsor or Designee	Mechanism for Reporting	Back-Up Method of Reporting
SAE ^a – after participant’s study participation has ended and the investigator becomes aware	After participant’s study participation has ended	N/A	Promptly	SAE paper form	N/A
Pregnancy					
Pregnancy in female participants and female partners of male participants	After the start of study intervention	90 days after the last dose	Within 24 hours (see Section 8.3.2)	Pregnancy paper form	N/A
Product Complaints					
PC associated with an SAE or might have led to an SAE	Start of study intervention	End of study intervention	Within 24 hours of awareness	PC form	N/A
PC not associated with an SAE	Start of study intervention	End of study intervention	Within 1 business day of awareness	PC form	N/A
Updated PC information	—	—	As soon as possible upon site awareness	Originally completed PC form with all changes signed and dated by the investigator	N/A
PC (if investigator becomes aware)	Participation in study has ended	N/A	Promptly	PC form	

Abbreviations: AE = adverse event; CRF = case reporting form; ICF = informed consent form; N/A = not applicable; PC = product complaint; PET = positron emission tomography; SAE = serious adverse event.

^a SAEs after study participation should not be reported unless the investigator deems them to be possibly related to study treatment or study participation.

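### The C-SSRS is not marked at Visit 21, so Weeks 72 to 76 are the only open-label interval with no guaranteed look-back C-SSRS for completers

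*Protocol*

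**What the plan says.** Protocol 1.3 schedules one "C-SSRS screening/baseline" form at Visit 2 (Week 0). The row "C-SSRS since last assessment" is then marked at Visits 4, 6, 8 and 10 in the first open-label table. In the second table it is marked at Visits 12, 14, 16, 18 and 20, at early termination (ET), and at 801-804. The Visit 21 cell is blank.

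On follow-up, the same table says: "Visit 801 to 804 may be used for return to baseline ADA monitoring and other safety assessments at discretion of the sponsor". Protocol 4.1 gives follow-up a maximum length but no minimum.

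Protocol 8.2.4 states: "Baseline assessment of SIB and intervention-emergent SIB will be monitored during Study AACN using the C-SSRS". It also asks that participants be "observed closely for SIB or any other unusual changes in behavior, especially at the beginning and end of the course of intervention". It sets no C-SSRS frequency.

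Protocol 4.1 adds: "The maximum duration of treatment is 72 weeks". The C-SSRS is one of the listed safety assessments in Protocol section 3.

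**The concern.** Each look-back form asks about the time since the previous one. A skipped visit therefore does no harm as long as a later form is certain to be completed. Visit 21 is the one skipped open-label visit with no such form after it. Someone who stops early gets a closing C-SSRS at ET; someone who completes does not, and the documents give no reason for the difference.

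At stake is a short stretch at the end of the open-label period in which suicidal ideation or behavior in a completer would be recorded only through ordinary event reporting, and not through the structured instrument the protocol names. It matters mainly for participants still being dosed near Week 72: the aducanumab arm, and donanemab participants who never met the plaque stopping rule.

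**Working it through.** The plan gives no figure to reproduce. The check is a reading of the schedule with simple counting.

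**Inputs (Protocol 1.3)**
- Visits 2 to 21 are four weeks apart, Weeks 0 to 76: 20 visits, so 19 between-visit intervals.
- The baseline form is at Week 0. Look-back forms are at Weeks 8, 16, 24, 32, 40, 48, 56, 64 and 72.
- The tolerance at Visits 20 and 21 is ±7 days each.
- Visits 801-804 fall in Weeks 84 to 120.
- Column alignment: the adverse event row is marked in all 12 columns of the second table, so the blank C-SSRS cell does belong to Visit 21.

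**1. Coverage.** Nine look-back forms, each spanning 8 weeks, give 9 × 8 = 72 contiguous weeks, or 72 / 4 = 18 intervals. The remainder is 19 − 18 = 1 interval, Visit 20 to Visit 21.

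**2. Size.** 76 − 72 = 4 weeks, and 4 / 76 = 5.3%. Guaranteed coverage is 72 / 76 = 94.7%.

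**3. With visit windows.** Shortest: 28 − 7 − 7 = 14 days (2 weeks). Longest: 28 + 7 + 7 = 42 days (6 weeks).

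**4. Next possible form.** The earliest follow-up visit is nominally 84 − 72 = 12 weeks after Visit 20, and only if requested. If held, its form would look back to Week 72 and close the gap.

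**5. Visit 21 against ET.** Ten rows are marked at ET:

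| Row | ET | Visit 21 |
|---|---|---|
| Physical/neurological exam | X | X |
| Concomitant medications | X | X |
| Adverse events | X | X |
| C-SSRS look-back | X | blank |
| Vital signs | X | X |
| Florbetapir PET | X | X |
| Hematology and chemistry | X | X |
| PK sample | X | X |
| ADA sample | X | X |
| Exploratory biomarkers | X | X |

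Nine of the ten match.

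**6. After the fix.** With a form at Week 76, coverage is 76 / 76 weeks (100%).

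**The case against.** The strongest reply is that nothing in the protocol is broken. Section 8.2.4 asks for close observation at the end of intervention but does not require a C-SSRS form there, and an every-second-visit pattern ends naturally at Visit 20. A form is completed at Week 72, the stated treatment maximum. The pre-dose weight row for aducanumab, which also ends at Visit 20, supports that as the last dosing visit. Other routes of capture remain. Visit 21 has an adverse event review and an exam. AE and SAE collection stops only when "Participation in study has ended" (Protocol 8.3.1), with SAEs reported within 24 hours. Section 8.2.4 also calls for a risk assessment whenever signs of suicidal ideation or behavior appear. The blank is the same in both arms, so the schedule builds in no imbalance. All of this stands, and it limits the point to a minor one. It does not remove the mismatch with the ET column.

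A reader might infer four stronger things that the documents do not support.

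- **That section 8.2.4 is violated.** It sets no frequency.
- **That the gap grows if Visit 21 is a dosing visit.** The schedule does mark an infusion there, which conflicts with the 72-week maximum. That is a separate inconsistency. The interval from Visit 20 to Visit 21 is the same length either way, and a look-back form at Visit 21 could not cover time after it.
- **That completers go without a C-SSRS until late in follow-up.** That assumes the sponsor requests no visit until the end of the Week 84 to 120 range, which the documents do not say.
- **That donanemab participants who stop under the plaque rule lose monitoring when their treatment ends.** They "stop donanemab infusions but continue all other assessments for the remaining duration of the open-label period and short-term follow-up period", and the scheduled forms run to Week 72, at least 72 − 52 = 20 weeks after the deciding scan.

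**Conclusion.** The point holds as a minor gap in safety completeness. For completers, one of 19 open-label intervals (Weeks 72 to 76) has no guaranteed look-back C-SSRS. This rests on two readings: that the blank at Visit 21 is as printed, which the column alignment supports, and that 801-804 are discretionary, as the schedule's note says.

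The effect on the planned C-SSRS summaries cannot be determined, because SAP 4.7.7 leaves the visit limits of the treatment window as placeholders (Y1 to Y2). The documents give no event rate from which to estimate missed events. Efficacy, power and alpha are unaffected.

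**What to change.** Mark the look-back C-SSRS at Visit 21 in the Schedule of Activities, so that completers get the same closing assessment as early terminators.

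The cost is one short questionnaire at a visit that already includes an exam, adverse event review, laboratory samples and a PET scan. It also means asking the study partner to attend that day, since Protocol 5.1 requests a partner's presence whenever the C-SSRS is given.

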To evaluate the safety and tolerability of donanemab vs aducanumab	Characterization of standard safety assessments: 
 • Spontaneously reported AEs • Clinical laboratory tests • MRI (ARIA and emergent radiological findings) • Serious hypersensitivity reactions • C-SSRS

Abbreviations: AD = Alzheimer's disease; AE = adverse event; ARIA = amyloid-related imaging abnormalities; C-SSRS = Columbia Suicide-Severity Rating Scale; MRI = magnetic resonance imaging; PET = positron emission tomography.

NOTE: Other pre-specified, non-gated endpoints not listed will be detailed in the SAP.

Overall Design

Study I5T-MC-AACN (AACN) is a Phase 3, open-label, head-to-head study to evaluate the superiority of donanemab to aducanumab in participants with early symptomatic AD.

Brief Summary:

Study AACN is a multicenter, randomized, open-label, head-to-head, Phase 3 study of donanemab compared to aducanumab in participants with early symptomatic AD.

Participants who meet entry criteria will be randomized in a 1:1 ratio to 1 of the following treatment groups:

- donanemab: 700 mg IV Q4W for first 3 doses and then 1400 mg IV Q4W
- aducanumab: Refer to PI/routine clinical practice

The maximum total duration of study participation for each participant, including screening and the post-treatment follow-up periods, is up to 127 weeks:

- Lead-In: any time prior to complete screening
- Complete Screening: up to 7 weeks
- Open-label study period: 76 weeks
- Follow-Up: up to 44 weeks

The maximum duration of treatment is 72 weeks.

Scheduled Reduction of Donanemab

Participants randomized to donanemab whose amyloid plaque reduction as measured by florbetapir F18 PET scans at Visit 8 (Week 24) or Visit 15 (Week 52) meets criteria will stop donanemab infusions but continue all other assessments for the remaining duration of the open-label period and short-term follow-up period. These dose reduction rules are defined by the sponsor.

Participants randomized to aducanumab will continue monthly infusions throughout the open-label period, regardless of amyloid plaque reduction on florbetapir F18 PET scans.

Participant randomization will be stratified by amyloid burden at baseline and ApoE ϵ 4 status (noncarrier/heterozygous/homozygous).

Number of Participants:

Approximately 200 participants will be randomly assigned to study intervention.

Intervention Groups and Duration:

[figure not shown]
Intervention Name	donanemab	aducanumab

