Vital signs	X	X	X	X	X	X	X	X	X	X	X	X	Vital signs include pulse rate, blood pressure, and temperature. Vitals should be measured after participant has been sitting for at least 5 minutes. Vital signs are measured prior to and within 30 minutes after infusion for clinical management, and not recorded in the CRF.
Weight (for aducanumab participants only)	X	X	X	X	X	X	X	X	X				Weight is measured prior to dosing with aducanumab only and is not recorded in the CRF.

	Open-Label Treatment											Short-term Follow-up	Comments
Visit Number	12	13	14	15	16	17	18	19	20	21	ET	801-804^	^Visit 801 to 804 may be used for return to baseline ADA monitoring and other safety assessments at discretion of the sponsor and may be requested within the time period listed.
Weeks relative to first infusion	40	44	48	52	56	60	64	68	72	76	-	84-120	
Visit interval tolerance (days)	±7	±7	±7	±7	±7	±7	±7	±7	±7	±7	-	±14	
MRI		X											MRI at V13 is to be performed and reviewed prior to V13 infusion. The MRI should occur at least 14 days after infusion at V12 is administered, and may occur outside of the visit windows. Unscheduled MRIs may be performed at the discretion of investigator, for example, if titration is delayed due to temporary suspension of infusions.
Florbetapir F18 PET scan				X						X	X		Collect at ET only if ET occurs at 3 or more IP infusions after the last florbetapir F18 PET scan.
Laboratory Tests and Sample Collections	In the event that study intervention is delayed, all laboratory collections should occur on the same day as study intervention infusion - and should be collected prior to infusion.												
Hematology and clinical chemistry				X						X	X		Collect prior to infusion.
PK sample				X						X	X	X	Collect prior to infusion. Predose collections may be collected from the IV site prior to the infusion.
Immunogenicity (ADA) samples				X						X	X	X	Collect prior to infusion.

	Open-Label Treatment											Short-term Follow-up	Comments
Visit Number	12	13	14	15	16	17	18	19	20	21	ET	801-804^	^Visit 801 to 804 may be used for return to baseline ADA monitoring and other safety assessments at discretion of the sponsor and may be requested within the time period listed.
Weeks relative to first infusion	40	44	48	52	56	60	64	68	72	76	-	84-120	
Visit interval tolerance (days)	±7	±7	±7	±7	±7	±7	±7	±7	±7	±7	-	±14	
Stored Samples													
Exploratory biomarker samples				X						X	X		Collect prior to infusion.

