7.3. Lost to Follow up

A participant will be considered lost to follow-up if he or she repeatedly fails to return for scheduled visits and is unable to be contacted by the study site. Site personnel or designee are expected to make diligent attempts to contact participants who fail to return for a scheduled visit or were otherwise unable to be followed up by the site.

Site personnel, or an independent third party, will attempt to collect the vital status of the participant within legal and ethical boundaries for all participants randomized, including those who did not get investigational product. Public sources may be searched for vital status information. If vital status is determined to be deceased, this will be documented and the participant will not be considered lost to follow-up. Sponsor personnel will not be involved in any attempts to collect vital status information.

8. Study Assessments and Procedures

- Study procedures and their timing are summarized in the SoA.
- Immediate safety concerns should be discussed with the sponsor immediately upon occurrence or awareness to determine if the participant should continue or discontinue study intervention.
- Adherence to the study design requirements, including those specified in the SoA, is essential and required for study conduct.
- All screening evaluations must be completed and reviewed to confirm that potential participants meet all eligibility criteria. The investigator will maintain a screening log to record details of all participants screened and to confirm eligibility or record reasons for screening failure, as applicable.

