10.11. Appendix 11: Protocol Amendment History

The Protocol Amendment Summary of Changes Table for the current amendment is located directly before the Table of Contents (TOC).

Amendment a: (11-Oct-2021)

Overall Rationale for the Amendment:

This amendment allows for better characterization of the incidence and severity of ARIA at an earlier time point.

Section # and Name	Description of Change	Brief Rationale
1.3. Schedule of Activities	Modified “Weeks relative to randomization first infusion ”.	Clarification. Visits should be scheduled in relation to the first IP infusion.
	Changed V3 interval tolerance from “±7” days to “-7 to +10” days.	To provide additional time to perform and review MRI prior to infusion.
	Added line to collect weight for aducanumab participants.	Aducanumab uses weight-based dosing. Weight is not recorded in the CRF.
	Added MRI at V3. Added text to the Comments field about MRI at V3, including text about MRI timings relative to the first and fourth infusions.	To allow for better characterization of the incidence and severity of ARIA at an earlier time point.
6.5. Dose Modification	Modified description of ARIA events in relation to dose modification and providing data for the ARIA Related Events CRF.	Clarification.
6.8.1. Medications for Alzheimer’s Disease	Added “When medically indicated, initiation, increase, or discontinuation of symptomatic treatments for AD is permitted.”	Clarification.
7.1.3. Amyloid-Related Imaging Abnormalities (ARIA)	Added note “While most cases of ARIA-E are asymptomatic, serious cases have been reported. Available data suggest serious cases are most likely to occur early in	To provide additional information.

Section # and Name	Description of Change	Brief Rationale
	dosing, after the first, second, or third infusion.”	
	Added cross-references to the Manual of Operations regarding information about temporary and permanent discontinuation guidance.	To provide further guidance.
	Modified text regarding considerations related to reinitiating study intervention..	Recommendation of DMC.
	Added instructions to complete the ARIA Related Events CRF in the event of symptomatic ARIA-H.	To provide instructions.
8.2.5. Magnetic Resonance Imaging	Added text to allow performance of unscheduled MRIs.	Clarification.

11. References

- Aducanumab-avwa package insert. Available at: https://www.accessdata.fda.gov/drugsatfda_docs/label/2021/761178s000lbl.pdf. Published on: Jun 2021. Accessed on 21 Jul 2021.

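### The Schedule of Activities marks an infusion at Visit 21 (Week 76), one dose past the 72-week treatment maximum, with no aducanumab dosing weight scheduled for it

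*Protocol*

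**What the plan says.** **Treatment limit.** Protocol Sections 1.1 and 4.1 state: "The maximum duration of treatment is 72 weeks". Section 4.2 and the SAP Introduction both place up to 72 weeks of treatment inside a 76-week period, so the two durations are meant to differ.

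**Infusion row.** In Section 1.3, the grid for Visits 12 to 21 marks "Administer study intervention" at all ten visits from Visit 12 (Week 40) to Visit 21 (Week 76). The early termination column and the Visits 801–804 column are blank. Weeks are counted from the first infusion. The comment on the row says that "Administration of study intervention (and treatment-related activities conducted in person) outside of the visit window is not a protocol deviation", unless two doses fall less than 21 days apart.

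**Weight row.** The same grid marks weight for aducanumab participants at Visits 12 to 20 and leaves Visit 21 blank. Its comment reads: "Weight is measured prior to dosing with aducanumab only and is not recorded in the CRF". The amendment history (Section 10.11) gives the reason for the row: "Aducanumab uses weight-based dosing".

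**After Visit 21.** The follow-up column runs from Week 84 to Week 120 and is optional: "Visit 801 to 804 may be used for return to baseline ADA monitoring and other safety assessments at discretion of the sponsor".

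**Aducanumab continuation.** Sections 1.1 and 4.1 also say that aducanumab infusions go on monthly for the whole open-label period whatever the PET result. No end week is given.

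**The concern.** The opening of Section 8 says: "Adherence to the study design requirements, including those specified in the SoA, is essential and required for study conduct". A site that works from the grid will therefore dose at Week 76, and a site that works from the text will stop at Week 72. It cannot do both.

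What is at stake is operational and concerns safety:

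- The surplus dose is of a drug with known ARIA and hypersensitivity risk, in either arm.
- No florbetapir scan is scheduled after Visit 21, so the dose serves no efficacy endpoint.
- The only exception named in the infusion row's comment is a gap of less than 21 days. A dose 28 days after Visit 20 would not be caught by it.
- Aducanumab is dosed by weight, and no weight is scheduled at Visit 21.
- If the sponsor requests no follow-up visit, Visit 21 is the participant's last visit. Under Section 8.3.1, routine adverse event collection stops when "Participation in study has ended". Serious events judged possibly related remain reportable after that.

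No new gap in ARIA monitoring is claimed, because the last scheduled MRI is already at Visit 13.

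**Working it through.** **1. Where the marks fall.** The grid for Visits 12 to 21 has 12 columns before the comments: Visits 12–21, early termination, and 801–804.

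| Row | Marks | Blanks | Total | Columns marked |
|---|---|---|---|---|
| Infusion | 10 | 2 | 12 | V12–V21 |
| Weight (aducanumab) | 9 | 3 | 12 | V12–V20 |
| Florbetapir PET | 3 | 9 | 12 | V15, V21, early termination |
| MRI | 1 | 11 | 12 | V13 |

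Every row fills 12 cells, and the PET and MRI marks agree with the accompanying text. A shifted infusion mark is therefore unlikely, although the source table itself was not seen. Over both grids (Visits 2–21, 20 columns) the infusion and weight rows agree in 19 columns. Visit 21 is the only mismatch.

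**2. Number of infusions.** With dosing every 4 weeks from Week 0, number of doses = last dosing week / 4 + 1.

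- Text (last dose Week 72): 72/4 + 1 = 19.
- Grid (last dose Week 76): 76/4 + 1 = 20.
- Excess: 20 − 19 = 1 dose, 4 weeks past the limit.

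**3. Does another reading of 72 weeks remove the conflict?** SAP Section 4.7.1 defines exposure as last dose date minus first dose date plus 28 days.

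| Last dose | Doses | First to last dose | SAP exposure |
|---|---|---|---|
| Week 68 | 68/4 + 1 = 18 | 68 weeks | 68 + 4 = 72 weeks |
| Week 72 | 19 | 72 weeks | 72 + 4 = 76 weeks |
| Week 76 | 20 | 76 weeks | 76 + 4 = 80 weeks |

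If the 72 weeks are counted from first to last dose, the grid exceeds them by one dose. If they are counted as SAP exposure, the last dose would be Week 68 and the grid exceeds them by 20 − 18 = 2 doses. The Week 76 infusion is over the limit on both readings. The first fits the weight row, which ends at Week 72, and is the one used here.

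**4. Contact after the dose.** Each infusion from Visit 2 to Visit 20 has a scheduled visit 4 weeks later. After Visit 21 the earliest possible visit is at Week 84: 84 − 76 = 8 weeks, and only if the sponsor asks for it.

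**5. Number of surplus doses.** At most one per participant, so at most 200 with about 200 randomized. The donanemab stopping rule and discontinuations lower this by an amount the documents do not give.

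**6. A related cell.** In the Visits 2–11 grid the MRI row has marks under Visits 3, 5, 8 and 11, while its comment gives instructions for Visits 3, 5, 8 and 10. The summary of changes for the current amendment also names Visit 10. As read, the fourth mark is one visit (4 weeks) late. This needs checking against the source table and does not bear on the main point.

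**The case against.** The strongest reply is that the documents do not establish which side is wrong. Aducanumab is to continue for the whole open-label period, which is 76 weeks. The grid's heading over Visit 21 refers to open-label treatment, the SAP calls the 76 weeks the treatment period, and the Visit 21 laboratory rows ask for collection before the infusion. On this view the sponsor should reconcile the two rather than delete the mark.

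These cues do not support a Week 76 dose:

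- The continuation sentence contrasts aducanumab with the donanemab stopping rule. It names no end week and does not cover donanemab, for which Visit 21 is marked as well.
- The SAP sentence that speaks of 76 weeks separates them from the 72 weeks of treatment.
- The grid heading also covers early termination, where no infusion is marked. The pre-infusion laboratory comments also cover early termination and, for PK and antibody samples, Visits 801–804.

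Other objections have some force. The Section 8 sentence binds sites to all design requirements, and the 72-week limit is one of them, so the grid does not override the text. That leaves sites with two conflicting instructions. SAP Appendix 1 lists a dosing algorithm violation as a significant violation, so a Week 76 dose could still be picked up there; the point about the row comment is confined to that comment. Investigators are told to consult the aducanumab label for the dose, so a missing weight mark does not mean that a participant goes unweighed. The weight row counts mainly as evidence of what was intended. The loss of follow-up arises only if a Visit 21 dose is given and no later visit is requested. The MRI item shows that a row can have the right number of cells and still carry a mark that disagrees with the text, so the cell count alone is not proof of intent. The four statements of the limit and the weight row supply the rest.

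**Conclusion.** The concern holds. The Visit 21 infusion mark is wrong as written: it schedules a 20th infusion at Week 76 where the text allows treatment up to Week 72, which is 19 infusions. The excess is one dose for each participant still on treatment and dosed by the grid.

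This rests on two assumptions: that the extracted grid reproduces the source table, and that 72 weeks runs from first to last dose. The other available reading makes the excess two doses.

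The 6-month co-primary analysis, the alpha allocation, the power and the exposure and compliance formulas do not change. The point should still be fixed, because it is a dosing instruction and following it gives an unintended dose with only discretionary follow-up.

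**What to change.** - In Protocol Section 1.3, Visits 12 to 21, delete the Visit 21 mark in the infusion row, so that Visit 20 (Week 72) is the last infusion.
- In Sections 1.1 and 4.1, add Week 72 as the end point to the sentence on continued aducanumab infusions.
- Check the fourth MRI mark in the Visits 2–11 grid against the source table. If it stands under Visit 11, move it to Visit 10.

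The cost is one table cell and a short phrase in two places at the next amendment, one more cell if the MRI mark is confirmed, and a communication to sites. There is no statistical cost.
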